
C. Approach

Design and Overview. This pilot study will examine the feasibility, acceptability, and preliminary impact of providing an In vivo intervention with NRT to increase NRT adherence compared to the control group. The intervention will be tested and refined initially with 10 participants in the In vivo NRT group (In vivo). Following the pre-pilot testing, 80 participants will be randomized to either the 1) In vivo or 2) Standard of Care (SC). All participants will complete approximately 60 minutes of baseline assessment to determine smoking history and characteristics prior to randomization, including previous experience with NRT. In vivo participants will be provided with each of the four forms of acute NRT (gum, lozenge, nasal spray, inhaler per week; counterbalanced across sessions by participant) to use in each 30 minute session in conjunction with a nicotine patch. In session, they will discuss their In vivo experience of using each combination NRT at each of the four sessions. To bolster their in vivo NRT experience, participants will be provided with a weekly sample of each NRT product to use between sessions to acclimate to the medication and to make PQAs. After the 4 week In vivo intervention period, participants will select their preferred acute NRT product to use with the nicotine patch (combination NRT; cNRT) to use for cessation over the next eight weeks. SC participants will receive four sessions of standard behavioral smoking cessation counseling and will select their preferred acute NRT (gum, lozenge, nasal spray, inhaler) based on product description. Thus, both groups will receive cNRT for 8 weeks total to make a quit attempt. All participants will continue to receive medication and monitoring for side effects, regardless of their medication adherence. Study visits occur at baseline (Week 0), intervention Weeks 1-4, medication selection/quit goal setting visit at Week 5, medication check (Week 6) Weeks 9 and 13 (end-of-treatment), and follow-up at one month later (Week 17; see Figure 1 for Study Design).

[figure not shown]
Preliminary Studies. The PI and her team have completed studies directly relevant to the current proposal and have worked with several different low income and disadvantaged populations such as individuals in the criminal justice system and Persons Living with HIV (PLWH).

Figure 1: Proposed Study Design from Recruitment to One Month Follow-up

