2. Prior Medication Use, Adherence, and Cessation. In a follow-up analysis, we examined prior use of bupropion in relationship to adherence and cessation. While only 26 participant (5%) reported prior use of bupropion, smokers with prior bupropion use were significantly more likely to rate bupropion as helpful for smoking cessation at baseline ($p=0.025$) compared to smokers without prior experience with bupropion. We ran univariate analyses to determine the factors associated with adherence. Of the almost 50 variables examined including demographics (age, sex, race, income, etc.), dependence, withdrawal, craving, and smoking history, (e.g., age of first smoking, number of previous quit attempts, etc.) only five variables were significantly associated with bupropion adherence: race, age, prior bupropion use, treatment group, and percentage of friends who smoke. When these variables were simultaneously entered into a logistic regression model, prior use of bupropion was the single best predictor of adherence (OR=3.50; CI: 1.45-8.47; $p=0.005$).

We examined univariate predictors of being abstinent (7 days abstinent, CO ≤ 3 ppm) at any time during treatment ("floating abstinence") and found several variables associated with abstinence including age, race, age of first tried smoking, cigarettes per day, abstinence self-efficacy, motivation, nicotine dependence, craving, difficulty of prior quit attempt, medication adherence, desire to quit in the next 30 days, and prior bupropion use. Using logistic regression, we found that medication adherence was the single best predictor of abstinence (OR=2.29; 1.32-3.97; $p=0.003$). Cigarettes per day was the only other variable associated with abstinence (OR=0.939; 0.898-0.981; $p=0.005$).

Given the associations between a) prior use of bupropion and medication adherence and b) medication adherence and abstinence, we were interested in testing a mediation model of these relationships. We found evidence of mediation such that the relationship between previous use of bupropion and smoking abstinence was significantly mediated by medication adherence (see Figure 2)⁵³. We also tested mediation models that included motivation to quit, abstinence self-efficacy, interest in quitting, and belief in the efficacy of bupropion

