To test Aim 3, we will examine medication adherence during the 8 week intervention period between the intervention groups using Chi Square analyses at weeks 6, 9 and 13. Medication adherence will be defined as a self-reported use of taking 80% of medication as prescribed at each time point for both groups (adherent or not adherent). We can also look at adherence as a continuous proportion variable: adherence = number of doses taken / the number of doses given. We will also examine demographic and smoking characteristics (particularly withdrawal, cravings, abstinence self-efficacy, and NRT perceptions) that would be associated with medication adherence at weeks 6, 9 and 13 using logistic regression. These analyses will allow us to examine important associations with medication adherence in these groups.

To examine underlying factors believed to be important for medication adherence, particularly withdrawal, craving, self-efficacy, and perceptions of NRT, we will also examine these factors by intervention groups across time using paired t-tests, as appropriate. We are primarily interested in determining if our In vivo group had decreases in withdrawal and cravings, while increasing abstinence self-efficacy and NRT perceptions relative to the SC group. Given the pilot nature of this intervention, we will be able to examine 24-hour quit attempts and abstinence, but these factors are not the main focus on analyses as we will likely be underpowered to find significant differences on these outcomes with this small of a sample. While 80 participants may seem like a fairly large sample for a pilot study, a sample size between 500-600 participants is typical for most smoking cessation interventions and would be needed to examine important moderators and mediators of cessation. However, we will be able to obtain initial effect sizes that will be useful for determining the appropriate sample size for a fully-scaled R01 project in the future, if this intervention appears promising.

Missing data. There is a high likelihood that we will have participants who may miss an appointment, do not complete the study, or are otherwise lost to follow-up. Because of the potential of bias due to non-missing

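### The adherence comparison between arms is an unadjusted chi-square, although prior NRT use is to be collected at baseline and could be adjusted for with a small gain in precision

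*SAP*

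**What the plan says.** The Aim 3 text in the SAP (Data Management and Statistical Analysis) compares adherence "between the intervention groups using Chi Square analyses at weeks 6, 9 and 13", with participants classed as adherent or not. No covariate is named. Two further analyses are mentioned. One is optional and has no test attached: "We can also look at adherence as a continuous proportion variable". The other looks for characteristics "that would be associated with medication adherence at weeks 6, 9 and 13 using logistic regression", with emphasis on cravings, withdrawal, self-efficacy and views of NRT. Neither is described as a comparison of arms adjusted for baseline, and prior medication use is not named in either. No stratification is described in the SAP's Randomization paragraph or in the Protocol's Random Assignment section.

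The SAP's Preliminary Studies (item 2) reports that "prior use of bupropion was the single best predictor of adherence" (odds ratio 3.50, CI 1.45 to 8.47), and adds that "only 26 participant (5%) reported prior use of bupropion". It then generalises in words from bupropion to concrete experience of a medication.

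Previous NRT use is to be recorded. The SAP's Design and Overview places the baseline assessment "prior to randomization, including previous experience with NRT", and Table 1 puts previous cessation treatment in the Smoking History form. The Baseline and Assessment Measures paragraph calls previous NRT use a proposed mediator or moderator, not an adjustment covariate. In the Protocol (Baseline Appointments, Procedures, steps 10 and 11), group assignment comes first and the participant completes the baseline questionnaires afterwards.

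**The concern.** The trial rests on the idea that experience with a medication raises adherence to it. Past NRT use is not an exclusion (only current use is), so some participants will arrive with the experience that the intervention supplies. With 80 participants and no stratification, the arms may differ by chance in how many such people they hold. The unadjusted difference carries that imbalance as part of its sampling error. The SAP means to use the effect sizes from this pilot to size a larger trial, so avoidable noise in the estimate has some cost. Adjusting for a prognostic baseline variable is the usual remedy, and this variable is already on the planned forms.

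**Working it through.** **Checking the plan's own figures.** The SAP gives no power calculation for 80, so there is none to reproduce. The odds ratio can be checked: SE = ln(8.47/1.45)/3.92 = 0.450; z = ln(3.50)/0.450 = 2.78; p = 0.0054, against a stated 0.005. Prevalence: 26/500 = 5.2%, against a stated 5%. Both agree.

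**Inputs.** Adherence 42.1% vs 20% (combination NRT at Week 4 in the sponsor's pilot, SAP Preliminary Studies item 3). 40 per arm, or 28 per arm at the planned 70% retention. Assumed: two-sided alpha 0.05, 1:1 allocation, odds ratio 3.50 for prior use in both arms, prevalence q of prior NRT use from 5.2% (the bupropion figure) to 50%.

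**Unadjusted power.** z = [d√n − 1.96√(2p̄(1−p̄))]/√Σp(1−p), with d = 0.221, p̄ = 0.3105 and Σp(1−p) = 0.1600 + 0.2438 = 0.4038. For n = 40: (1.398 − 1.283)/0.635 = 0.18, power 57.2%. For n = 28: 42.9%. Power of 80% needs 68 per arm.

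**Variance explained.** ρ² = q(1−q)·Σδ²/Σp(1−p), where δ is the adherence difference between prior users and others within an arm, set by the odds ratio and the arm's overall rate. Effective n = n/(1−ρ²). At q = 5.2%: δ = 0.259 (SC) and 0.299 (In vivo), Σδ² = 0.1565, so ρ² = 0.0493 × 0.1565/0.4038 = 0.019.

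| Prior use q | SC: others / prior users | In vivo: others / prior users | ρ² | Worth, of 80 | Power 40/40 | Power 28/28 |
|---|---|---|---|---|---|---|
| none adjusted | – | – | – | – | 57.2% | 42.9% |
| 5.2% | 18.7 / 44.5% | 40.5 / 70.5% | 1.9% | 1.6 | 58.0% | 43.6% |
| 10% | 17.5 / 42.6% | 39.1 / 69.2% | 3.4% | 2.8 | 58.7% | 44.2% |
| 30% | 13.5 / 35.3% | 33.0 / 63.3% | 7.2% | 6.2 | 60.5% | 45.7% |
| 50% | 10.6 / 29.4% | 27.3 / 56.9% | 7.6% | 6.5 | 60.6% | 45.9% |

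Across the confidence limits of the odds ratio and q from 5.2 to 50%, power at 40/40 runs from 57.3% (odds ratio 1.45) to about 67% (8.47). The Protocol lists five groups; if that meant 4:1 allocation, 35.3% would become 35.9 to 38.1% at odds ratio 3.50.

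**Simulation check (4,000 trials per setting, odds ratio 3.50, 40/40).** Chi-square power was about 57%. The adjusted likelihood-ratio test gave 59.4%, 61.0% and 62.8% at q = 5.2%, 20% and 50%; Cochran-Mantel-Haenszel (CMH) gave 57.8%, 59.3% and 61.1%. Type I error over 40/40 and 28/28 was 4.2 to 5.3% (chi-square), 4.9 to 5.9% (likelihood ratio) and 4.4 to 5.0% (CMH), so part of the likelihood-ratio gain is a slightly liberal test. A separate simulation with treatment odds ratio 2.9 gave 55.1% to 57.4% at q = 30% and 56.4% to 59.4% at 50%.

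**Chance imbalance.** SD of the difference in prior use = √(2q(1−q)/40): 5.0 points at 5.2% and 10.2 at 30%, so 95% ranges of about ±10 and ±20 points. At 30%, each 10 points of imbalance moves the unadjusted difference by 10 × (0.218 + 0.303)/2 = 2.6 points, or about 5 points at the edge of that range. The 95% half-width of the unadjusted difference is 1.96 × √(0.2438/40 + 0.1600/40) = 19.7 points.

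**Sparsity.** At 5.2%, 4.2 of 80 participants are expected to be prior users. At least one arm has none with probability 2(0.948)^40 − (0.948)^80 = 22% (40% at 28/28). In simulation the covariate effect could not be estimated (no prior users, or all with the same outcome) in about 24% of trials (41% at 28/28).

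**The case against.** Four stronger readings are tempting, and the documents support none of them.

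- A reader might infer that chance imbalance biases the test or can pass for a treatment effect. It cannot in that sense: under randomisation it is part of sampling error, and chi-square type I error was near 5%. A 2.6-point shift is small beside a half-width of about 20 points.
- A reader might take prior NRT use to be a proven strong predictor of NRT adherence. The figure is for prior bupropion use and bupropion adherence, in a community-corrections trial with 26 exposed people. It was found after screening almost 50 variables and is probably inflated. Transfer to NRT is inference, though the SAP draws it too.
- A reader might expect a gain of 7 to 8% of variance. That needs prevalence of 30 to 50% and the same odds ratio in both arms. In vivo participants will all have sampled four products before the eight-week treatment period, so earlier use may matter less there. In the limiting case where it acts only in SC (q = 30%), the common slope is 0.218/2 = 0.11, a 10-point imbalance moves the difference by 1.1 points, and variance explained is 2 × 0.21 × 0.109²/0.4038 = 1.2%.
- A reader might think adjustment costs nothing. If prior use is rare, its effect may not be estimable. Under the Protocol's order of steps, the item could also be answered after the group is known.

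It is also fair to say that the planned logistic regression could include prior use as a smoking characteristic. It remains an exploration of correlates, and the factors that it stresses are repeatedly measured targets of the intervention. Their post-baseline values cannot serve as adjustment covariates. What stands is that no adjusted arm comparison is prespecified.

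**Conclusion.** The point holds as a minor improvement in precision. The planned chi-square is valid; an adjusted comparison using one variable already on the planned forms would be modestly more precise and would absorb chance imbalance in prior experience. At the only prevalence in the documents (5%, for bupropion) the gain is about 2% of variance and 1 power point. At an assumed 30 to 50% with a common odds ratio of 3.50 it is 7 to 8% and about 2 to 3 points; the slightly liberal likelihood-ratio test showed up to about 5. The result assumes 1:1 allocation, two-sided alpha 0.05, the pilot's adherence rates, and transfer of the bupropion odds ratio to NRT. Adjustment does not repair the larger limitation, which is power of 43 to 57% at the planned size.

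**What to change.** In the Aim 3 text, prespecify at each of weeks 6, 9 and 13 a logistic model for adherence with two terms: arm and prior NRT use (yes/no). Report the standardised (marginal) risk difference with its 95% CI, which keeps the estimate on the scale of a difference in proportions, where an adjusted odds ratio would not. Keep the chi-square as the unadjusted companion.

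State a fallback in advance, for example when there are no prior users at a visit or all of them have the same outcome, and name it: the CMH test or the unadjusted comparison. Leave no optional covariates.

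Reconcile the Protocol's baseline procedure with the SAP's Design and Overview and Randomization paragraphs, so that prior NRT use is recorded before assignment.

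The cost is SAP wording, a little extra analysis, and possible recourse to the fallback if prior use is rare. No new data item is needed.

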## **Brief Purpose of Study**

This study is designed to examine whether In Vivo nicotine replacement therapy (NRT) experience intervention will be effective in quitting smoking as compared to behavioral standard of care smoking cessation treatment. For this study, In Vivo experience is: the use of one of four different short-acting NRT products in conjunction with nicotine patches during session. Specialized counseling focused around the experience of NRT, including how the use of NRT may help with quitting smoking, side effects, and smoking cessation expectancies will also be utilized.

If eligible to participate, subjects will be randomized into one of the four Intervention (In-Vivo) groups or the control group. They will be asked to fill out forms regarding smoking behavior, demographics, medical information, and a contact sheet. Some questionnaires will be repeated at every visit and others will be repeated less frequently. Participants are asked to complete 13 weeks of intervention, comprised of five weeks of smoking cessation therapy (Intervention or Control; Weeks 1-5) and three treatment sessions designed to measure medication adherence (Weeks 6, 9 and 13). Following intervention completion, participants will be asked to return for a follow up visit at one month.

Participants in the Intervention groups will be asked to go as long as they can without smoking the day of the therapy sessions. They will put a nicotine patch on during each of the weekly sessions. During the first four weekly sessions, participants in the Intervention groups will also use a different form of short-acting NRT each week (nicotine gum, lozenge, inhaler, nasal spray) and in the fifth week, will select which short-acting medication they would prefer to use for the duration of the study. Participants will discuss the experience of wearing the patch and/or using the short-acting NRT while they are in session. The Control group will not use NRT medication during the sessions but will be given standard counseling regarding quitting smoking.

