### Subject Enrollment

#### Inclusion Criteria

- At least 18 years old
- Qualifying as low income (making <150% above the poverty line, or <\$22,260 as a single, or <\$45,570 for a family of four)
- Smoked at least 10 cigarettes per day (CPD) for the last year
- Live in an unrestricted environment (e.g., living in a halfway house, or independently)
- Expire carbon monoxide (CO) >8 ppm at Baseline
- Positive cotinine test at Baseline

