## Procedures

1. Go through the Consent Form with the participant, addressing any questions or concerns they may have.
2. Have the participant sign and date where it states “Signature of Participant” on page 6 of the Consent Form. Make sure that they also sign on page 7 (Authorization for Use/Disclosure of Personal Health Information (PHI) for Research), on which they need to print their name at the top of the page and sign/date at the bottom of the page where it says “Signature of Participant.”
3. Be sure that you also sign the consent form on page 6 as the “Person Obtaining Consent.”
4. The participant will receive one signed copy of the consent, and we will keep one signed copy for our records.
5. Administer the CO test. Refer to the CO directions under the “Carbon Monoxide Monitor” section on page 8 of this manual.
6. Place a lid on urine cup and take the participant to the restroom for the urine screen.
7. After the participant uses the restroom, have them hand you the cup so that you can administer the pregnancy test (for women only) and the cotinine test. After these tests, you should discard the urine sample and all tests and head back to the office.
8. Have the participant complete the contact sheet.
9. Set up the participant in the Pre-Randomization arm.
10. Once the Pre-Randomization is completed, complete the last form remaining in REDCap, “Group Assignment,” to randomize the participant into one of the groups.
11. Once the participant is randomized into a group, have the participant fill out the Baseline questionnaires for that group on the tablet or on the computer in an office. Do not allow them to fill out in waiting room or any other office where we are not present.
12. Monitor the participant’s progress in REDCap.
13. Schedule the first intervention session for the following week, at least 5 days from Baseline. Also, it is important for participants in the Intervention groups to be scheduled for their weekly appointment in the morning. Once you have it scheduled, make sure the appointment is placed on your UABMC calendar and google calendar (MOP, pg. 14).
14. Instructions for participants for Session 1 are as below, according to which group they have been assigned:
  - If the participant is in an **Intervention** group then say, “**When you come in for your appointment on \_\_\_\_\_ at \_\_\_\_\_ please refrain from smoking the night before your appointment, and the morning of.**”

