  - If the participant is in the **Control** group, there are no special instructions for the next appointment.

15. Complete the \$10.00 ClinCard payment.
16. Give the participant an appointment card. That completes the Baseline appointment!

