Intervention. In vivo Group. Participants in the intervention group will receive In vivo experience with four different forms of short acting NRT combined with patch and counseling focused on their experience of using NRT, including positive experiences, side effects and smoking cessation expectancies. For each session, participants will be instructed to arrive to session wearing the nicotine patch and to have gone as long as possible without smoking. The rationale for instructing patch use from the beginning is to promote the use of combination NRT as the expectation. Further, instructing participants to go as long as possible without smoking is to demonstrate the additive effect of short acting NRT for relieving cravings and withdrawal effects. Prior to each session and receipt of the short acting NRT, participants will complete the brief withdrawal (Minnesota Nicotine Withdrawal Scale [MNWS]) and craving (Questionnaire of Smoking Urges; QSU) measures; see Table 1 for a brief description. Participants will repeat these assessments at the end of their session. All sessions (In vivo or SC) will be approximately 30 minutes and will be conducted individually by research assistants (RAs) trained to use the In vivo manual and who are not tobacco treatment specialists to increase real-world application and dissemination of this approach (see In vivo manual in Appendix A).

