Session 1: At the end of the Baseline assessment (described below), In vivo participants will be given one nicotine patch and instructed to place it on their upper arm the day of their next appointment. If they arrive without the patch, they will immediately have a patch placed on their upper arm. They will then complete the assessment measures to allow the nicotine patch to demonstrate initial medication effects. The peak effects of nicotine patch occurs at 3.8 hours; however, initial detection of the drug occurs at 11.8 minutes⁵⁵. Thus, participants will be wearing the patch for at least 30 minutes of assessment or longer which should be sufficient to experience at least some of the effects of the patch for relieving withdrawal. Our pilot work demonstrated that In vivo participants experienced reduced withdrawal and craving within 30 minutes of administration. After assessment, the first few minutes of the intervention will focus on their in vivo experience of wearing the nicotine patch and will query previous experiences with the patch. We will solicit both positive (e.g., “the patch helps with cravings”) as well as negative perceptions (e.g., “it makes my arm itch”) of the patch. Participants will discuss any side effects they experience with using the nicotine patch in session. Next, participants will be given one of four short-acting forms of NRT (gum, lozenge, inhaler, nasal spray; counterbalanced across participants by session). Thus some participants may receive gum first, while others will receive inhaler, lozenge, or nasal spray. This will wash out any primacy or recency effects of NRT across participants for product selection. The gum, lozenge and inhaler demonstrate initial effects for relief of withdrawal around 5 minutes and peak effects after about 15 minutes, while the nasal spray occurs more rapidly and more closely mimics the relief from smoking⁵⁶⁻⁵⁷. Thus, the delivery of nicotine in these short-acting products should be fast enough for participants to experience the effects of the medication on withdrawal and craving symptoms during session, as we noted with gum in our previous pilot study. Safety and efficacy results specific to both the patch and the specific short-acting NRT administered will be reviewed with the participant. They will also discuss their expectancies for the effectiveness of these products for cessation. Participants will be given a week supply of nicotine patches and whichever short-acting product they were randomized to receive first to use

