
after session and will be instructed on its use. The purpose of providing a seven day supply of cNRT product will be to encourage participants to use and acclimate to the cNRT and to use for PQAs. They will not be required to abstain during the week, but can use the cNRT however they wish, which may include concurrent use with smoking, or during practice or legitimate quit attempts. They will be instructed to wear the patch the day of their Session 2-4 visits but not to use the short-acting NRT on the day of study visits.

Sessions 2-4: Before completion of assessment measures, participants will be checked to make sure they are wearing a nicotine patch and will have a patch placed on their upper arm if they are not wearing it. After the assessment, they will be asked about their experience during the past week with using the nicotine patch and their experience with their short-acting NRT product, including any positive or negative experiences with the either medication and how they have used the NRT (e.g., to reduce) as well as any quit attempts they experienced. After this point, they will be given the next short-acting nicotine product and provided instructions on how to use the medication in session. They will discuss any prior experiences using the specific short-acting NRT as well as their expectancies for the medication to reduce their withdrawal or cravings. Safety and efficacy information specific to the use of that specific short-acting NRT will be reviewed with the participant. They will discuss any side effects that they notice with use of the specific short-acting NRT in session. Similar to above, participants will be given a week supply of both the patch and the assigned short-acting NRT at each session to use for practice during the week. They will always be instructed to wear a patch but not use the short-acting NRT during the morning of their subsequent sessions.

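### Only In vivo participants are asked not to smoke before the Week 1-5 visits, and the Aim 3 withdrawal and craving comparison does not set those visits apart

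*SAP*

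**What the plan says.** **Smoking before visits.** The SAP (Intervention, In vivo Group) says that for each session "participants will be instructed to arrive to session wearing the nicotine patch and to have gone as long as possible without smoking". It gives the reason: to let participants feel what the short-acting product adds. The manual's Baseline script (Procedures, step 14) tells Intervention participants to "please refrain from smoking the night before your appointment, and the morning of". Step 13 adds that "it is important for participants in the Intervention groups to be scheduled for their weekly appointment in the morning". For Control, step 14 says "there are no special instructions for the next appointment".

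**Patch before visits.** The SAP (Session 1) says "In vivo participants will be given one nicotine patch and instructed to place it on their upper arm the day of their next appointment", and for later sessions "They will always be instructed to wear a patch but not use the short-acting NRT during the morning of their subsequent sessions". The manual (Brief Purpose of Study) says of the Intervention groups "They will put a nicotine patch on during each of the weekly sessions". Its Baseline materials and steps include no patch.

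**Baseline state.** The manual's entry criteria include "Expire carbon monoxide (CO) >8 ppm at Baseline", and nothing restricts smoking before that visit in either arm.

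**Analysis.** The last part of Aim 3 (SAP, Data Management and Statistical Analysis) examines withdrawal, craving, self-efficacy and NRT perceptions by group over time, with paired t-tests where appropriate. The stated interest is whether withdrawal and craving fell in In vivo relative to standard care (SC). The text names no visits, does not separate within-session from across-visit change, and does not mention the unequal arrival instructions.

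**The concern.** Reduced withdrawal and craving is one of the mechanisms through which the SAP expects sampling to improve adherence. A between-arm comparison of these scores is interpretable only if the arms are measured in comparable states, or if the difference in state is declared to be part of what is being estimated. At Weeks 1-5 the In vivo pre-session score follows requested abstinence. The SC score and every Baseline score do not.

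The two natural readings of the analysis are pushed in opposite directions:

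- **Across visits:** In vivo moves from unrestricted smoking at Baseline to requested abstinence, so its scores tend to rise and the comparison counts against it.
- **Within session:** the raised starting score leaves more room to fall, so the comparison counts for it.

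Because the plan does not choose a reading, either conclusion about the mechanism could come partly from the instruction. Adjusting for the pre-session score would not remove this, since that score is measured after randomization and is itself moved by the instruction.

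**Working it through.** The documents give no power, effect size or SD for MNWS or QSU, so there is no planned figure to reproduce. The check is textual, followed by an illustration of scale.

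**1. Instructions by arm.** The manual has 4 intervention groups x 4 weeks = 16 closing reminders for Weeks 1-4.

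| Item | In vivo | Control |
|---|---|---|
| Baseline script asks for no smoking before Week 1 | yes | no |
| Week 1-4 reminders ask for no smoking the night before | 16 of 16 | 0 of 4 |
| Week 1-4 reminders forbid a patch that morning | 15 of 16 | not applicable |

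The exception is Group A, Week 2, step 25, which names only the inhaler.

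**2. Visits affected.** The Baseline script governs Week 1, and the Week 1-4 reminders govern Weeks 2-5. That is 5 of the 8 on-treatment visits with MNWS and QSU (Weeks 1, 2, 3, 4, 5, 6, 9 and 13). The Week 5 steps contain no request to abstain before Week 6, so the instruction does not reach Weeks 6, 9 and 13.

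**3. What the named test answers.** A paired t-test compares two scores within one group. It cannot test whether the change in In vivo differs from the change in SC, which is the stated question. The illustration below therefore uses a between-arm t-test of change.

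**4. Scale, across visits.** Assumptions: SD 1 at each visit, Baseline-session correlation r = 0.5, no treatment effect, and an instruction that raises the In vivo score by d. The allocation ratio is also assumed. The SAP randomizes 80 between two arms without stating a ratio, while the manual randomizes to four intervention groups plus Control. I show 40 v 40 (1:1) and 64 v 16 (five equal groups).

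- SE = sqrt(2(1 - r)) x sqrt(1/n1 + 1/n2)
- 40 v 40: SE = 1 x sqrt(2/40) = 0.224
- 64 v 16: SE = 1 x sqrt(1/64 + 1/16) = 0.280

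The chance that In vivo appears significantly worse is the upper tail of a noncentral t with 78 df and noncentrality d/SE, in a two-sided 5% test (nominal 2.5% in that tail):

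| d (SD) | 40 v 40 | 64 v 16 |
|---|---|---|
| 0.1 | 6% | 5% |
| 0.2 | 14% | 11% |
| 0.3 | 26% | 18% |
| 0.5 | 60% | 42% |

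For d = 0.3 and 40 v 40, changing r from 0.4 to 0.7 moves the figure from 23% to 40%.

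The paired test named in the SAP, applied within In vivo alone (n = 40, SE = 1/sqrt(40) = 0.158), would show a significant rise in 23%, 46% and 87% of trials at d = 0.2, 0.3 and 0.5.

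**5. Within session.** The direction follows from the raised start. I put no number on it, because it would need a second assumption about how much of the rise is relieved in 30 minutes.

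**6. Patch.** Under both documents a patch is on before the pre-session questionnaires, because the SAP has one applied on arrival if it is missing. The difference is how long it has been worn. It is clearest at Week 1, when the manual has dispensed none. Up to 30 minutes of wear is 30/228 = 13% of the SAP's 3.8 hours (228 minutes) to peak. Under the SAP, application 1-2 hours before arrival (assumed; no time is given) plus 0-30 minutes of questionnaires gives 60/228 to 150/228 = 26-66%.

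**The case against.** The strongest reply is that requested abstinence is a declared part of the In vivo package, with its purpose stated. A larger in-session fall is then partly what the package is meant to produce, and calling it bias presupposes a different estimand. This stands for the within-session contrast. That contrast can be reported if it is labelled as the effect of the whole package, abstinence included. It does not rescue the Baseline-to-session contrast, where the instruction raises withdrawal and craving, the reverse of the fall the analysis is looking for.

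Second, the shift has no anchor in the documents. Participants are asked to try, compliance is unknown, and take-home NRT at Weeks 2-5 may offset it. This stands in full: the percentages show sensitivity and do not estimate what will happen.

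Third, this is a flexible secondary analysis in a pilot, and silence about visits does not prove that Week 1-5 scores would be compared with Baseline. That is fair, but the SAP's own pilot reported in-session falls relative to SC, so use of these scores is a realistic prospect.

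A reader might also infer that the manual leaves In vivo abstinence largely without patch cover throughout Weeks 1-5. The documents support that only for Week 1. Later reminders forbid the patch on the morning of the visit, participants hold a week's supply, and wear on the previous day or night is not barred.

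**Conclusion.** The point holds as a cheap improvement to a secondary, mechanism-oriented analysis. The arms are given different arrival instructions at 5 of 8 on-treatment visits. The plan neither excludes those visits from a comparison with SC nor names a test that makes that comparison. The direction of distortion depends on the reading chosen. Its size is unknown: about 14-60% (40 v 40) or 11-42% (64 v 16) false findings against In vivo if the shift is 0.2-0.5 SD, and 5-6% if it is 0.1 SD, against 2.5%. All of these rest on assumed shifts, r = 0.5 and an assumed allocation ratio.

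The patch conflict is separate and real, but it concerns duration of wear, not whether a patch is on.

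It would be tempting to conclude that the trial's main result is compromised. The documents do not support that: feasibility, acceptability and adherence at Weeks 6, 9 and 13 do not use these scores. Nor do they support treating the abstinence request itself as a design error.

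**What to change.** 1. In the Aim 3 text, define the between-arm withdrawal and craving test as MNWS and QSU at Weeks 6, 9 and 13, In vivo versus SC, adjusted for the Baseline score (ANCOVA at each visit, or one mixed model with arm by visit). Do not present Week 6 as preceding adherence, because Week 6 is also an adherence endpoint.
2. State that Week 1-5 pre-session scores are not evidence of change from Baseline relative to SC. Report Week 1-5 pre-post change descriptively in both arms, labelled as the effect of the whole package including requested abstinence. Keeping the SC pre-post data preserves the only control for time and session effects.
3. Tabulate CO, time since last cigarette and overnight abstinence by arm at Weeks 1-5, to show how far the arms differed on arrival. SAP Table 1 already lists these items.
4. Confirm which patch instruction staff deliver. The SAP is dated later than the manual's last listed amendment, so the manual should not be presumed correct. Then make the two documents agree, including the Group A Week 2 reminder.

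The cost is text edits and one table. No new data are needed, since MNWS and QSU are already scheduled at Weeks 6, 9 and 13 in both arms. The price is that Weeks 1-5 no longer contribute to the between-arm mechanism test.
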